### **7.4 ACCESS TO THE FINAL TRIAL DATASET**

The CCO Investigators and statisticians will have full access to the study data-set. Data generated by LENS will be available to bona fide researchers via the Richard Doll Centenary Archive (see <https://www.ndph.ox.ac.uk/about/richard-doll-centenary-archive>) which has a Data Access and Sharing Policy.

### **7.5 ARCHIVING**

The CCO will retain trial data and records for at least 25 years (identifiable data for 10 years) after the end of the trial except in the case of any documentation which is legally required to be retained in Scotland in which case such documents will be stored at the University of Glasgow under the required conditions. Regulatory Authorities will have the right, in accordance with GCP guidelines, to commission a confidential audit of such records while the trial is in progress or thereafter.

## **8 MONITORING, AUDIT & INSPECTION**

The trial will be conducted in accordance with the principles of the International Conference on Harmonisation Guidelines for GCP, and relevant local, national and international regulations (including the EU Clinical Trials Directive).

Monitoring will be based on the study's risk assessment and will be detailed in the study Monitoring Plan. The Monitoring Plan will be agreed by the Trial Management Group (TMG) and TSC. The Monitoring Plan will consist of both central monitoring and on site monitoring, both of which will be conducted and overseen by the CCO.

Prior to the initiation of the study at any site, it will be verified that the LCC has adequate facilities and resources to carry out the study (and, if considered necessary, a site visit will be undertaken). Local PIs and Research Nurses will be provided with materials detailing relevant study procedures, and the LCC will be trained in study methods.

Monitoring visits at LCCs are intended at the following stages: around site set-up, by the end of month 12, by the end of month 30, and around month 48 in preparation for site closure. If, an on-site visit cannot be accommodated at approximately these time points, the site will be asked to complete a review of their Investigator Site File and confirm completeness. During on-site visits, the LCC staff are expected to be present. Where an on-site visit coincides with a participant study visit, the monitor may be present during the interview (subject to the participant's verbal agreement) to provide ongoing training in study procedures such as consent taking and the use of the study eCRF. The purpose of site visits is to help LCC staff to resolve any local problems with the study, to ensure that the study is conducted according to the protocol, and to review study records and data quality and provide any additional training that may be required. A report of each visit will be prepared by the study monitor and reviewed by CCO staff.

Central monitoring of the study data will be performed to confirm data completeness, timely entry and to identify any outliers in relation to study matrix e.g. recruitment rates, reporting of events. This central monitoring will be used to direct any non-routine site visits.

If any party becomes aware of an upcoming audit or inspection, the monitoring team at the CCO should be informed. The CCO will advise what preparation may be required and will suggest appropriate personnel to support the audit/inspection.

## **9 ETHICAL AND REGULATORY reports and CONSIDERATIONS**

Before the start of the trial, approval will be sought from a REC for the trial protocol, ICFs and other relevant documents. Substantial amendments that require review by REC will not be implemented until the REC grants a favourable opinion (unless failure to do so would introduce risk to participant/s in the opinion of the investigator). Correspondence with the REC will be retained in the Trial Master File and Investigator Site Files (ISF). Annual progress reports will be submitted to the REC within 30 days of the anniversary date on which the favourable opinion was given, and annually until the trial is declared ended. It is the CI's responsibility to produce the annual reports as required and to notify the REC of the end of the study. Within one year after the end of the study, the CI will submit a final report with the results to the REC.

### **9.1 PEER REVIEW**

Prior to submission for funding, the trial proposal was internally reviewed by one expert ([name], University of Glasgow). The full trial application to NIHR underwent peer review by seven independent experts, and the trial's design was modified based on their comments and suggestions.

### **9.2 PUBLIC AND PATIENT INVOLVEMENT**

On 18th March 2015, two LENS investigators met with 15 members of the Glasgow South Diabetes UK Group to present and discuss LENS. The members advised on patient perceptions of the research question and practicalities of delivering the trial. They indicated that they understood the need for a control group. Two patients with diabetes have volunteered to join the TSC as patient representatives and these individuals will be involved with preparing and reviewing study information and providing patient perspectives on the trial's conduct. The Royal National Institute for the Blind (RNIB), Scotland, is also supporting the trial in terms of dissemination of information and results of the trial, review of materials, lay summaries and newsletters, and representation on the TSC. Feedback regarding the various PILs to be used in the trial and the content of

questionnaires will be sought from the Glasgow South Diabetes UK Group and/or other patient support groups.

### **9.3 AMENDMENTS**

The sponsor may make a non-substantial amendment at any time during a trial. If the sponsor wishes to make a substantial amendment to the CTA or the documents that supported the original application for the CTA, the sponsor will submit a valid notice of amendment to the MHRA. If the sponsor wishes to make a substantial amendment to the REC application or the supporting documents, the sponsor must submit a valid notice of amendment to the REC for consideration. It is the sponsor's responsibility to decide whether an amendment is substantial or non-substantial. Amendments will be notified to NHS Research & Development departments of participating sites to assess whether the amendment affects the NHS permission for that site. The CI will be responsible for the decision to amend the protocol.

### **9.4 COMPLIANCE**

#### **9.4.1 Protocol compliance**

Protocol deviations, violations, or breaches are departures from the approved protocol. Prospective, planned deviations or waivers to the protocol are not allowed under the UK regulations on Clinical Trials and must not be used. Accidental protocol deviations must be documented and reported to the CI.

#### **9.4.2 Regulatory Compliance**

The trial will not commence until a Clinical Trial Authorisation (CTA) is obtained from the MHRA. Before any site can enrol patients into the trial, the local PI or designee will apply for and obtain permission from the site's NHS Research & Development (R&D) department.

#### **9.4.3 Notification of Serious Breaches to GCP and/or the protocol**

A "serious breach" is a breach which is likely to affect to a significant degree the safety or physical or mental integrity of the subjects of the trial; or the scientific value of the trial.

In the event that a serious breach is suspected, the CCO and CI must be contacted within 1 working day. It is the CI's responsibility to contact the Sponsor without delay. In collaboration with the CI, the serious breach will be reviewed by the Sponsor and, if appropriate, the Sponsor will report it to the REC committee, Regulatory authority and the NHS host organisation within seven calendar days.

### **9.5 FINANCIAL AND OTHER COMPETING INTERESTS**

The trial investigators and research team have no conflicts of interest regarding the conduct of the trial.

### **9.6 INDEMNITY**

The University of Oxford has a specialist insurance policy in place which would operate in the event of any participant suffering harm as a result of their involvement in the research (Newline Underwriting Management Ltd, at Lloyd's of London). NHS indemnity operates in respect of the clinical treatment that is provided.

## 10 DISSEMINATION POLICY

On completion of the trial, the data will be analysed and tabulated and a Final Study Report prepared. Funding organisations will be acknowledged in all resultant publications. Participants will be informed of the main results of the trial with a newsletter or letter. The protocol will be made publically available on the NIHR website during the conduct of the trial and will also be included as a supplementary file at the time of publishing the main trial results.

Draft copies of manuscripts will be circulated to all co-investigators and local PI for their review prior to submission for publication. Results from the trial will be published in the name of the LENS collaboration.

The design paper, primary LENS results publication and subsequent publications will be submitted for publication in medical journals in an open access format. RNIB will cover the trial results on their webpage and via other strategies. The results will be submitted for presentation at appropriate conferences.

## 12 APPENDICES

### 12.1 APPENDIX 1 - RISK ASSESSMENT

A risk assessment of the trial was performed prior to final sign-off of the contract with the funder. This risk assessment is a controlled version working document which is subject to change. It is stored in EDMS, the document management system of CTSU. The risk assessment will form the basis of the Trial Monitoring Plan.

## 12.2 APPENDIX 2 – AUTHORISATION OF LOCAL COLLABORATING CENTRES

### 12.2.1 Required documentation

Prior to opening a LCC, the following essential documentation will be provided to the sponsor:

- Evidence of local R&D approval
- An original signed Investigator Declaration (signed by the local PI as part of Clinical Trial Agreement documentation)
- A signed and dated recent CV for the local PI and research nurse
- Copies of GCP certificates for the local PI and research nurse

### 12.2.2 Procedure for initiating/opening a new site

Trial staff from the RCC (or from the CCO where this is not possible) will perform training for the local PI, research nurse and any other staff involved in the trial at the LCC.

### 12.2.3 PI responsibilities

The local PI at each site is responsible for the overall conduct of the study at their site and for compliance with the protocol and any protocol amendments. Responsibilities may, however, be delegated to an appropriate member of study site staff. Delegated tasks will be documented on a Delegation Log and signed by all those named on the list. The local PI must be familiar with the IMP, protocol and the study requirements.

## 12.3 APPENDIX 3 – SCHEDULE OF ASSESSMENTS

PROCEDURE	Screening Visit	Randomisation visit	Subsequent telephone / email follow-up (every 6 months for at least 3 years unless stated otherwise)
Informed consent	X		
Inclusion / exclusion criteria	X	X	
Record demographics	X	X	
Medical History	X	X	
Lifestyle factors	X		
Concomitant medications	X	X	
Height		X	
Weight		X	
Vital signs		X	
Blood eligibility biochemistry	X a	X a	
Blood HbA1c	X		
Blood lipids (random)	X		
Urine albumin creatinine ratio	X		
Trial-specific Questionnaire (by telephone or medical records)			X
EQ-5D questionnaire (on paper)	X		X d
VFQ-25 questionnaire (on paper)	X		X d
Open-label fenofibrate mail-out (10 week supply)	X b		
Blinded drug mail-out (26 week supply)		X	X
Compliance with study treatment		X	X
Randomisation		X c	
Willingness to start and/or continue study treatment	X	X	X

a U&E, LFTs (including at least one of ALT and AST), CK

b run-in drug mail-out will not be immediate as it will first be necessary to verify biochemistry; the initial mail-out of open-label fenofibrate will be followed by a phone call 2-3 weeks later to verify receipt by the participant

c randomisation will not occur at the time of the visit as it depends on visit biochemistry; starting dose frequency will depend on renal function

d for completion after 24 months and then at the final assessment

## 12.4 APPENDIX 4 – PROTOCOL AMENDMENT HISTORY

Substantial / non-substantial amendment	Protocol version no.	Date issued	Author(s) of changes	Details of changes made
Approved by REC	2.0	21-09-2016	[name] [name]	
 
Section 4.8: removal of need to provide written confirmation of withdrawal
 
Section 3.2.3: expansion of potential exploratory endpoints for OCT
 
Minor clarifications or corrections to text on pages 27, 29, 32, 35, 47, 56
 

Substantial amendment 1	3.0	26-04-2017	[name] [name]	
 
Additional method of recruitment – via HIC
 
Revision of section 5 –Safety reporting
 
Change from registered to routine postal delivery of study treatment
 
Clarifications or corrections to text throughout the document
 

Substantial amendment 2	4.0	07-07-2017	[name] [name]	
 
Revised wording in section 4.4.4 to clarify procedural steps for recruitment using HIC services.
 

Substantial amendment 3	5.0	05-10-2017	[name] [name] [name]	
 
P.3 Key Trial Contacts – addition of [name]
 
Section 3.2 – movement of text
 
Section 4.4.2 – addition of a telephone call to potential participants to ask if they would be interested in receiving information about LENS and seek verbal consent to check key eligibility criteria in their health records (specifically their most recent eGFR result and retinal screening results).
 
Section 4.5.1 – correction of 6-10 to 6-11 weeks
 
Section 4.11 – updating Manufacturer's Authorisation; inclusion of plan to provide low HDL-c data to DMC
 
Section 5.3 – clarification regarding AE reporting
 

Substantial amendment 4	6.0	10-01-2018	[name] [name]	
Changes added based on MHRA review:
 
 
Section 4.11.12 – Clarification regarding true abstinence
 

				
 
• Sections 4.2.2, 4.11.10, 4.11.11 – Exclusion criterion added: rosuvastatin 40mg daily
 
• Section 4.5.10 – Refinement of creatine kinase assessment prior to randomisation
 
• Section 4.6.6 – Clarification regarding unblinding
 
• Section 4.8.1 – Addition of list of circumstances which will lead to cessation of study treatment
 
• Section 5.3.3 – Clarification regarding reporting urgent safety measures
 

Non-substantial amendment 2	6.1	12-02-2019	[name] [name]	
Minor edits:
 
Addition of collaborators (p4)
 
Exclusion criteria clarified to make distinct the biochemical eligibility for each face-to-face assessment visit and for lack of adherence to run-in treatment (4.2.2)
 
Clarification regarding timing of call to check receipt of run-in drug (4.5.3)

Non-substantial amendment 4	6.2	29-05-2020	[name]	
Remove treatment duration (summary)
 
Clarify minimum trial duration (summary; section 2)
 
Allow for DRS grading to not change (footnote to Table 1)
 
Clarify that evidence of clinically significant DR may come from retinal imaging or clinical examination (3.2.1, Table 2)
 
Adjudicate vitreous haemorrhage (3.3)
 
Remove comment on discrepancy between data sources (3.3)

Non-substantial amendment 5	6.3	06-01-2021	[name]	
Participants will not complete follow up questionnaires on their own devices; follow up by medical records to be used where necessary (4.6.1, 4.7, 5.3.1, 7, 12.3)
 
EQ-5D and VFQ-25 will only be completed on paper (4.5.1, 4.7, Table 3, 12.3)
 
Source data to be retained for 25 years, but identifiable data for 10 years after trial (7.1, 7.5)

				Clarify description of introduction of OCT by NHS Scotland (Table 1 and footnote) Update site monitoring plan in context of COVID pandemic
Substantial amendment 5	7.0	29-07-2022	[name]	
Remove signature page (protocol is signed off in the EDMS system)
 
Change [name] details (page 3)
 
Remove [name] (page 3)
 
Include details of change in NHS Scotland management pathway for M2 maculopathy: Section 1, Table 1
 
Use consistent wording to describe M2, R3 and R4 as 'referable' disease (rather than 'clinically significant' or 'significant' disease): Trial summary, Sections 3, 4.2 and 6.1; Table 2
 
Diabetic Retinal Screening (DRS) update to Diabetic Eye Screening (DES) after NHS Scotland change to program name: various Sections
 
DES definition for blot (vs. dot) haemorrhage added: Table 1
 
Clarification that M2 includes blot haemorrhages (which has always been the case): Trial summary, Sections 3.1.2, 3.2.2; Table 2
 
Include plans for use of image analysis software at a later stage: Section 3.2
 
Allow for future meta-analyses of all fenofibrate trials: Section 3.2.4
 
Minor grammatical correction 4.11.13
 
Shorten heading Section 5.3
 
Correct reference to UK GDPR and Data Protection Act 2018: Section 7.3
 
It was not possible to offer the option for participants to complete follow up forms on their own devices, line removed: Section 4.5.1.
 
Show details of amendment numbers in Appendix 4

This Statistical Analysis Plan describes the strategy, rationale and statistical methods that will guide assessment of the clinical efficacy and safety of fenofibrate in the LENS trial.

3.1 Study design

LENS is a randomised placebo-controlled trial investigating the effects of prolonged treatment with the PPAR alpha agonist, fenofibrate on the progression of diabetic eye disease. At least 1,060 participants with observable diabetic retinopathy or maculopathy will be randomised (using a minimisation algorithm, see Appendix A: Details of randomisation algorithm) between oral fenofibrate 145mg or placebo tablets. Study treatment is taken once daily in the context of normal renal function, or as one tablet every second day in the context of reduced renal function. Follow up is scheduled to continue until at least 222 primary outcome events have occurred and median follow up (counting from the date of randomisation of the median participant) is at least 4 years.

The trial is designed to be streamlined. Most data for pre-specified efficacy outcomes is obtained by linkage to NHS Scotland records. Only the Screening and Randomisation assessments occur in person, and all subsequent assessments occur by telephone or by reference to medical records. Study treatment is mailed to participants' homes. After the initial Screening visit is conducted and safety blood tests are performed, eligible individuals (who are approved to enter the run-in by the local investigator) are provided with active fenofibrate 145mg tablets to be taken (daily with normal renal function, one tablet every second day with reduced renal function) for approximately 8 weeks. They are then asked to return to the study clinic for a Randomisation assessment. If they remain eligible based on information collected at this assessment and further safety blood tests, and are willing to continue, participants are randomly allocated to fenofibrate 145mg tablets or placebo.

No research blood or urine samples are taken from randomised participants. Linkage to NHS Scotland data-sets is performed to obtain results for HbA1c, renal function (serum creatinine, eGFR, urine albumin, urine albumin creatinine ratio) and other assays (e.g. lipids) that have been collected as part of routine care.

3.2 Study objectives

The primary objective of the LENS trial is to assess the effect of allocation to fenofibrate versus placebo on progression to the composite primary outcome of referable diabetic retinopathy (DR) or any of the following treatments for diabetic retinopathy: retinal laser therapy, vitrectomy or intra-vitreal injections (see Section 4.3).

Other objectives include assessments of the effects of fenofibrate on secondary outcomes (see Section 4.4), tertiary outcomes (see Sections 4.5) and longer term follow up outcomes (to be covered in a separate analysis plan at a later date).

4 Definitions for efficacy and safety endpoints

4.1 Estimands

For the efficacy and safety endpoints based on clinical events, the estimand of interest will be the rate of first occurrence of the endpoint in the target population allocated fenofibrate relative to the rate of first occurrence of the endpoint in the target population allocated placebo, conditional on the baseline covariates used in minimised randomisation, ignoring any non-fatal intercurrent events, and in the hypothetical absence of death from any cause not included in the efficacy or safety endpoint being assessed.

4.2 Hypotheses

For all statistical tests, the null hypothesis will be that the effect of allocation to fenofibrate on the endpoint of interest in the target population is the same as the effect of allocation to placebo.

4.3 Primary efficacy assessment

The primary assessment will involve an intention-to-treat comparison, among all randomised participants, of the effect of allocation to fenofibrate versus placebo on time to the first occurrence during the scheduled treatment period on the following composite primary outcome: the development of referable diabetic retinopathy^a or any of the following treatments for diabetic retinopathy: retinal laser therapy, vitrectomy or intra-vitreal injection of medication due to diabetic retinopathy

4.4 Secondary efficacy assessments

4.4.1 Secondary assessments based on clinical events

This will involve intention-to-treat comparisons among all randomised participants of the effects of allocation to fenofibrate versus placebo during the scheduled treatment period on time to the first occurrence of:

4.4.1.1 The composite primary outcome in various subgroups:

- Sex (male vs. female)
- Age at randomisation (< 60 years vs. \geq 60 years)
- Type of diabetes (Type 1 diabetes vs. Type 2 diabetes and other types)
- Renal function (randomisation assessment eGFR^b < 60 vs. \geq 60 mL/min/1.73m²)
- HbA1c (screening assessment HbA1c < 70 mmol/mol vs. HbA1c \geq 70 mmol/mol)
- First primary outcome in the first year vs subsequent years of follow-up (because of the known reduced impact of lipid modification on cardiovascular events, and potentially reduced impact of fenofibrate on laser treatment for diabetic retinopathy, in the first year of treatment^{1,2)}

4.4.1.2 The individual components of the composite primary outcome, namely:

- The development of referable diabetic retinopathy^a;
- Treatment for diabetic retinopathy: any of retinal laser therapy, vitrectomy or intra-vitreal injection of medication due to diabetic retinopathy

^a referable diabetic retinopathy is defined according to NHS Scotland's DES grading as R3 or R4 [excluding R4i as it represents inactive disease] or M2 in at least one eye in the DES grading scheme; such evidence may come from NHS retinal screening or clinical examination

^b as entered into the eCRF by research staff using whichever formula is employed by that NHS health board

LENS Statistical Analysis Plan

- 4.4.1.3 Any progression of diabetic retinopathy across the NHS Scotland retinopathy grading scale^c
- 4.4.1.4 The presence of hard exudates or blot haemorrhages within 1 disc diameter of the macula^d
- 4.4.1.5 Macular oedema

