### **3.2.4 Longer term follow up**

Consent will be sought from participants at baseline to facilitate investigation of the longer term effects of ~4 years' fenofibrate treatment after the main study ends. Long-term outcomes may include the development of significantly impaired vision or blindness, DR related eye procedures, cardiovascular outcomes, progression to end-stage renal failure and other outcomes. Any long term follow-up will be described in a further protocol and new ethical and Public Benefit and Privacy Panel (PBPP) approvals will be required before such work is undertaken (see section 4.6.5).

Where possible, we will seek to meta-analyse LENS results with results from FIELD and ACCORD and other trials of fenofibrate therapy.

**Table 2.** Summary of LENS objectives and outcomes

Objectives	Outcome Measures	Time-point(s) of evaluation
Primary Objective: to compare the effect of allocation to fenofibrate versus placebo on the primary outcome	Primary outcome: the composite of progression from observable DR to referable DR (defined according to the Scottish DES grading as R3 or R4 or M2 in at least one eye*), or any of retinal laser therapy, vitrectomy or intra-vitreal injection of medication due to DR, whichever occurs first.  * from retinal imaging or clinical examination	
 
6-12 monthly retinal screening;
 
6 monthly trial-specific questionnaires
 

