### 4.2 ELIGIBILITY CRITERIA

#### 4.2.1 Inclusion criteria

- Subjects capable of giving informed consent
- DM (any type except gestational diabetes)
- Age  $\geq 18$  years
- Observable DR (defined as R1 in both eyes or R2 in one/both eyes at the most recent retinal screening assessment; or M1 in one/both eyes at any retinal screening assessment in the 3 years prior to screening)
- Willing to either complete electronic questionnaires or conduct telephone interviews for collection of questionnaire data once every 6 months

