## 6 STATISTICS AND DATA ANALYSIS

### 6.1 SAMPLE SIZE CALCULATION

Availability of prospective NHS Scotland DES data allowed progression rates for DR to be calculated directly from the target population in which LENS will be conducted. Data in Table 6 indicate DR progression rates (limited to patients with at least 3 years' follow-up and a baseline result prior to 2009). If it is assumed that participants will be recruited from among the various grades with observable DR in proportion to their prevalence, the progression rate from observable to 'referable' DR would be approximately 29% over 4 years. On that basis, 1060 participants would yield approximately 222 events over an average follow-up of 4 years, providing 85% power to detect a 33% reduction in progression (allowing for 15% drop-out) at alpha = 0.05. We aim to randomise at least 1060 participants.

As described in LENS' inclusion criteria, patients with R1 DR will need to have bilateral rather than unilateral R1 given that progression rates to referable DR are 2.4X and 3.7X higher in type 1 DM and type 2 DM respectively with bilateral R1 compared with unilateral R1. Inclusion of patients with unilateral R1 would substantially reduce event rates.

The LENS composite primary outcome consists of progression of observable DR to referable DR, or any of retinal laser therapy, vitrectomy or intra-vitreal injection of medication due to DR. While DR progression is likely to dominate in terms of numbers of events, this composite outcome has been selected to avoid missing any unexpected rapid progression of DR which requires intervention before the next DES screening visit.

**Table 6.** Progression rates of DR in Scotland (baseline data pre-2009)

	Progression to referable retinopathy or maculopathy over 3 years*			
Baseline grading	M2	R3	R4	M2 or R3 or R4
Type 1 DM (n=14,354)				
R0 M0 (n=7,202)	131 (1.8%)	204 (2.8%)	12 (0.2%)	347 (4.8%)
R1 (one eye) M0 (n=2,480)	170 (6.9%)	21 (0.9%)	24 (1.0%)	215 (8.7%)
R1 (both eyes) M0** (n=4,016)	622 (15.5%)	121 (3.0%)	102 (2.5%)	845 (21.0%)
R2 or M1** (n=656)	237 (36.1%)	64 (9.8%)	48 (7.3%)	349 (53.2%)
Type 2 DM (126,639)				
R0 M0 (n=92,543)	942 (1.0%)	73 (0.1%)	82 (0.1%)	1,097 (1.2%)
R1 (one eye) M0 (n=20,147)	822 (4.1%)	62 (0.3%)	45 (0.2%)	929 (4.6%)
R1 (both eyes) M0** (n=11,978)	1,663 (13.9%)	264 (2.2%)	128 (1.1%)	2,055 (17.2%)
R2 or M1** (n=1,971)	530 (26.9%)	184 (9.3%)	60 (3.0%)	774 (39.3%)

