7.3 Subgroup analyses and tests for heterogeneity

The secondary assessments (see Section 4.4.1.1) include intention-to-treat analyses among all randomised participants of the effects of allocation to fenofibrate versus placebo during the scheduled treatment period on the primary outcome in sub-categories of patient based on categories of data collected at baseline. Tests for heterogeneity of the proportional effect observed in subgroups will be used to determine whether the proportional effects in specific subcategories are clearly different from the overall effect.^{2,3} (Note that for the subgroups that can be sensibly ordered [age, renal function and HbA1c] this test for heterogeneity is equivalent to a test for trend because each of the subgroups is to be split into only two categories [see Section 4.4.1.1].)

When many different subgroups are considered, chance alone may lead to there being no apparent effect in some subgroups considered in isolation, even when the effect of treatment really is about the same as is observed overall. In such circumstances, “lack of direct evidence of benefit” is not good “evidence of lack of benefit”, and clearly significant overall results would provide strong indirect evidence of benefit in subgroups where the results, considered in isolation, are not conventionally significant (or, even, perhaps, slightly adverse).³⁻⁵ Hence, unless the proportional effect in some specific subcategory is clearly different from that observed overall, the effect in that subcategory is likely to be best estimated indirectly by applying the proportional effect observed among all patients in the trial to the absolute risk of the event observed among control patients in that category.⁵

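### If fenofibrate works, the year-1 versus later-years contrast on the primary outcome is biased towards a weaker first-year effect, because the first follow-up image usually covers time before randomisation

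*SAP*

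**What the plan says.** SAP 4.4.1.1 includes "First primary outcome in the first year vs subsequent years of follow-up" in its list of subgroups. The reason given is pharmacological: a known early shortfall of lipid modification on cardiovascular events, and a "potentially reduced impact of fenofibrate on laser treatment for diabetic retinopathy, in the first year of treatment". The timing of detection is not mentioned.

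SAP 7.3 describes heterogeneity tests "on the primary outcome in sub-categories of patient based on categories of data collected at baseline". Year of event is not a baseline category, and no separate method is given for it.

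On imaging, Protocol 4.2.1 defines retinopathy eligibility as "R1 in both eyes or R2 in one/both eyes at the most recent retinal screening assessment". The schedule in Protocol Appendix 3 has no retinal image at the screening or randomisation visit. Protocol Table 2 gives "6-12 monthly retinal screening" as the time points for the primary outcome, and Protocol 4.1 leaves the standard care pathway unchanged. Protocol 3.2.1 expects most primary outcomes to come from routine imaging.

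**The concern.** The contrast treats the year in which an event is detected as if it showed when treatment acted. Randomisation trails the qualifying image. On the DES mail-out route the results letter arrives some weeks after the image (Protocol 4.4.3), and the randomisation visit comes 6-11 weeks after the trial screening visit (Protocol 4.5.6). The SDRN and HIC routes are not timed to an image, and no upper limit on image age is stated for the R1/R2 grades. Referable disease that develops between the last clear image and randomisation is found at the first image afterwards, usually in year 1, and dilutes the year-1 HR. Most later images close intervals that lie wholly after randomisation.

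The dilution runs in the direction the SAP is looking for. A drug that acts at once and constantly would, on average, look weaker in year 1, and this contrast could not tell it from a drug with a real lag.

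**Working it through.** **The plan's own figures.** Protocol 6.1 states that "the progression rate from observable to 'referable' DR would be approximately 29% over 4 years", and that "1060 participants would yield approximately 222 events over an average follow-up of 4 years". The power it claims for a 33% reduction is 85%, after 15% drop-out and at alpha 0.05.
- Events: 1060 × 0.85 / 2 × (0.29 + 0.29 × 0.67) = 218. With 0.67 applied as a hazard ratio, the fenofibrate risk is 1 − 0.71^0.67 = 0.205, giving 223.
- Power (Schoenfeld): √222 / 2 × |ln 0.67| − 1.96 = 1.02, which is 84.7%.
- Table 6, recruited groups: 4,023/18,621 = 21.6% at 3 years, or 28.8% at 4 years by linear scaling.

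The figures reproduce, so 29% at 4 years and HR 0.67 are used below.

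**Who is affected.** Bilateral R1 M0 makes up (4,016 + 11,978)/18,621 = 86% of the recruited groups in Table 6. Protocol Table 1 rescreens R1 at 12 months, so year 1 usually holds one image.

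**Expected year-1 HR.** Let g be the months from last clear image to randomisation, with 12-monthly images, a constant hazard, and HR 0.67 from the day of randomisation. To first order:

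year-1 HR = [g + 0.67 × (12 − g)] / 12

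If 2 months of run-in fenofibrate lower the hazard equally in both arms, the pre-randomisation exposure is g − 2 + 0.67 × 2 = g − 0.66, and:

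year-1 HR = [(g − 0.66) + 0.67 × (12 − g)] / [(g − 0.66) + (12 − g)]

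| g (months) | No run-in effect | With run-in effect |
|---|---|---|
| 3 | 0.75 | 0.74 |
| 4 | 0.78 | 0.77 |
| 6 | 0.84 | 0.83 |
| 9 | 0.92 | 0.91 |

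The later-years HR stays at 0.67.

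**Simulation.** 1,060 participants, 15% drop-out, 4 years, run-in effect included, 2,000 trials per row for the last two columns. 14% of participants have 6-monthly images, except in the 6-month row, where all are 12-monthly.

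| Gap (assumed) | Year-1 HR | Later HR | Year 1 weaker | Heterogeneity test rejects |
|---|---|---|---|---|
| None, no run-in (reference) | 0.68 | 0.68 | 51% | 4% |
| 3 months | 0.74 | 0.67 | 62% | 6% |
| 6 months | 0.82 | 0.67 | 78% | 10% |
| Uniform 3-9 | 0.81 | 0.68 | 77% | 12% |
| Uniform 3-12 | 0.88 | 0.67 | 83% | 16% |
| Uniform 3-9, true HR 1 | 1.01 | 1.01 | 50% | 5% |

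About 93% of year-1 detections close an interval that opened before randomisation. About 25% had their onset before randomisation at a 3-month gap, and about 52% at 3-9 months.

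**Variations.**
- Table 6 hazards by grade, with 6-monthly images for R2 and M1 (assumed for all M1): 0.78 vs 0.68 for gaps of 3-5.4 months, and about 0.85 vs 0.67 for 3-12 months. Rejection is about 7-13%.
- 20% of screens missed or delayed by one interval (assumed), gaps of 3-9 months: about 14% of later-year detections also close an interval that opened before randomisation. The HRs are 0.84 vs 0.68.

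**Size against noise.** With about 70 year-1 and 171 later events, the standard error of the log-HR difference is √(4/70 + 4/171) = 0.28. At a 3-month gap the bias is ln(0.745/0.668) = 0.11, about 0.4 of a standard error. For gaps of 3-12 months it is ln(0.880/0.666) = 0.28, about one standard error. The grade-specific version gives about 0.5 to 0.8.

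**The case against.** The strongest reply is that this is one noisy secondary contrast and the SAP already asks for caution. SAP 7.2 requires allowance for the number of secondary analyses. SAP 7.3 prefers the overall proportional effect unless a subcategory clearly differs. The version history names an exploratory analysis that excludes the first 12 months, and SAP 4.7 reports screening visits per arm. The gap is not documented. R2 (14% of the recruited groups together with M1, and 1,123/4,023 = 28% of their Table 6 events) is rescreened at 6 months, and procedure-based events are not tied to images.

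Much of this stands: it limits the size and the weight of the point. It does not remove the bias. None of these provisions separates carry-over from a true lag, and excluding year 1 leaves the year-1 estimate unexplained. The midpoint rule in SAP 7.4 is written for unknown event dates, not for the interval between two images.

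A reader might go further and infer that a reduced first-year effect must appear. It need not: the bias is in expectation only, it requires a working drug, and year 1 is not the weaker period in 17-38% of the simulated trials with a gap and a true effect. Nor would the drug be expected to show almost no effect in year 1. HRs of 0.74 and 0.88 keep ln 0.74 / ln 0.67 = 75% and ln 0.88 / ln 0.67 = 32% of the log effect. Nor does the SAP predict a weaker early effect on retinopathy; it calls one only potential.

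**Conclusion.** The concern holds as an expected bias in a secondary contrast. If fenofibrate works, the year-1 HR is diluted even with no lag: about 0.74-0.88 against 0.67-0.68 later, with the heterogeneity test rejecting in about 6-16% of trials instead of 5%. The direction follows from the documents. The size rests on an assumed gap of about 3-12 months, a constant hazard and a regular imaging cycle. Six-monthly screening and procedure-based events reduce it, and delayed screens, which SAP 4.7 acknowledges under COVID-19, move some of it into later years.

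A reader might infer that the primary result is compromised. The calculations do not support that. The overall HR is also diluted (0.69-0.73 in the simulations with a gap and a true effect), but at a true HR of 1 the overall test rejected in 5.0% of trials, so the primary intention-to-treat test remains valid.

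**What to change.** Keep the split, and make three additions.

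1. In SAP 4.4.1.1 and 7.3, state that a weaker year-1 HR is expected from the screening interval alone if the drug works, and is not by itself evidence of delayed action.
2. Report the time from last image to randomisation by arm.
3. Add a sensitivity analysis using DES image dates: a period-specific interval-censored proportional hazards model anchored on the last pre-randomisation image. Allow no treatment effect before randomisation, fit separate log HRs for 0-12 months and beyond 12 months, and test the difference between them.

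In 300 simulated trials per scenario with a constant HR of 0.67 and 12-monthly images, this model returned 0.66 and 0.67 for gaps of 3-5.4 months, and 0.65 and 0.66 for 0-12 months.

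The first two additions cost a sentence and a table row. The third needs modest programming, and its year-1 estimate is less precise (SD of the log HR about 0.27-0.32, against 0.23 for the simple split). At an SD of 0.32, a year-1 HR of 0.67 has a 95% interval of 0.67 × exp(±1.96 × 0.32), or 0.36 to 1.25. It removes the bias but will not settle the question of a lag, so it belongs beside the split and not in place of it.
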